6.2 Non-Study Vaccines

Not applicable.

6.3 Vaccine Preparation and Administration

The investigator or designee will be responsible for oversight of the administration of vaccine to subjects enrolled in the study according to the procedures stipulated in this study protocol. All vaccines will be administered only by unblinded personnel who are qualified to perform that function under applicable local laws and regulations for the specific study site. Expired vaccines must not be administered.

QIVc will be provided in pre-filled syringes (PFS), with an injectable volume of approximately 0.5 mL. Afluria Quadrivalent is supplied as a 0.25 mL and a 0.5 mL PFS. The full volume contained in the PFS is to be administered.

Standard immunization practices are to be observed and care should be taken to administer the injection intramuscularly into the anterolateral region of the thigh (for subjects 6 through 11 months, in general) or in the deltoid region (for subjects ≥ 12 months, in general).

Detailed vaccine preparation and administration instructions will be provided to investigators prior to study start.

It is recommended that 25 gauge, 25 mm (1 inch) of length needle is used for the vaccine administration.

PRECAUTIONS TO BE OBSERVED IN ADMINISTERING STUDY VACCINE:
Prior to vaccination, subjects must be determined to be eligible for study vaccination and it must be clinically appropriate in the judgment of the investigator to vaccinate. Eligibility for vaccination prior to first study vaccine administration is determined by evaluating the entry criteria outlined in protocol [Sections 4.1, Inclusion Criteria](#) and [4.2, Exclusion Criteria](#).

Eligibility for subsequent study vaccination is determined by following the criteria outlined in [Section 4.3, Criteria for Delay of Vaccination](#).

The study vaccines should not be administered to individuals with known hypersensitivity to any component of these vaccines.

Standard immunization practices are to be observed and care should be taken to administer the injection: Intramuscularly into the anterolateral region of the thigh (for subjects 6 through 11 months, in general) or in the deltoid region (for subjects \geq 12 months, in general). Before administering a vaccine, the vaccination site is to be disinfected with a skin disinfectant (eg, 70% alcohol). Allow the skin to dry. **DO NOT inject intravascularly or intragluteally.**

As with all injectable vaccines, trained medical personnel and appropriate medical treatment should be readily available in case of anaphylactic reactions following vaccine administration. For example, epinephrine 1:1000, diphenhydramine, and/or other medications for treating anaphylaxis must be available.

6.4 Vaccine Administration Error or Overdose of Vaccine

Vaccine administration error is defined as receiving a dose of study vaccine that was not reconstituted as instructed or administered by a different route from the intended route of administration. An overdose of study vaccine (whether accidental or intentional) is defined when a dosage higher than the recommended dosage (as per the QIVc dosing regimen referred to in [Section 6.1, Study Vaccine\(s\)](#) or as per the package insert of Afluria Quadrivalent®) is administered.

Any vaccine administration error or overdose of study vaccine detailed in this protocol must be reported as an adverse event, and if the vaccine administration error or overdose is associated with a SAE, it must be reported as such within 24 hours to the Sponsor.

6.5 Prior and Concomitant Medications and Vaccines

All medications, vaccines and blood products taken or received by the subject within 1 month prior to the start of the study are to be recorded on the Prior and Concomitant Medications eCRF.

In addition, the following are considered prior medications for this protocol: all medication/vaccines described in the inclusion and exclusion criteria of this protocol including:

- a) Influenza vaccination in the last 12 months.
- b) Systemic administration of corticosteroids (PO/IV/IM) within 90 days prior to informed consent.
- c) Administration of antineoplastic and immunomodulating agents or radiotherapy within 90 days prior to informed consent.

d) Received immunoglobulins or any blood products within 180 days prior to informed consent.

The use of antipyretics and/or analgesic medications within 24 hours prior to vaccination must be identified and the reason for their use (prophylaxis versus treatment) must be described in the source document and Concomitant Medications CRF. The use of antipyretics/analgesics within 24 hours prior to vaccine administration is a reason to delay study vaccination (see [Section 4.3, Criteria for Delay of Vaccination](#)).

Medications taken for prophylaxis are those intended to prevent the onset of symptoms. Medications taken for treatment are intended to reduce or eliminate the presence of symptoms that are present.

Concomitant medications include all medications (including vaccines with the exception of vitamins, minerals and alternative medicines) taken by/administered to the subject at and after enrollment continuing up to the end of the treatment period and must be documented on the Concomitant Medications eCRF. During the follow-up period, all vaccinations should be documented and only those concomitant medications are documented on the Concomitant Medications eCRF if associated with an SAE, NOCDs, or AE leading to study withdrawal.

When recording concomitant medications/vaccines, they should be checked against the study entry and continuation criteria in [Section 4, Selection of Study Population](#) to ensure that the subject should be enrolled/continue in the study.

A non-study influenza vaccination(s) is considered a protocol deviation if received during the study and may result in the subject being excluded from the Per Protocol Set (PPS)

6.6 Vaccine Supply, Labeling, Storage and Tracking

The Sponsor will ensure the following:

- Supply the study vaccine(s).
- Appropriate labeling of all study vaccines in compliance with the legal requirements of each country where the study is to be performed.
- Appropriate storage and distribution of study vaccines.

The Investigator must ensure the following:

- Acknowledge receipt of the study vaccines by a designated staff member at the site, including:
 - Confirmation that the vaccines were received in good condition and in the right amount.
 - Confirmation to the Sponsor that temperature range during shipment from the Sponsor to the Investigator's designated storage location in the correct range (2°C to 8°C / 36°F to 46°F).
 - Report any temperature deviation and do not use vaccines until further confirmation by the Sponsor or delegate that the vaccines are authorized for use.
- Proper storage of the study vaccines, including:
 - Storage in a secure, locked, temperature-controlled location.
 - Proper storage according to the instructions specified on the labels and in the Pharmacy Manual.
 - Appropriate record keeping and inventory of the study vaccines, including regular documentation of adequate storage temperature.
- Appropriate management of the study vaccines, including:
 - Non-use of vaccines in case of temperature deviation, prior to receipt of authorization for use from the Sponsor or delegate.
 - Use only in accordance with the approved protocol.
 - Proper handling, including confirmation that the vaccine has not expired prior to administration.
 - Appropriate documentation of administration of vaccines to study subjects including:
 - Date, dosage, batch/lot numbers, expiration dates, unique identifying numbers assigned to subjects and study vaccines, and time of vaccine administration. This information will be maintained in an accountability log that will be reviewed by the site monitor.
 - Reconciliation of all vaccines received from the Sponsor. Reconciliation is defined as maintaining records of which and how many vaccines were received, which vaccines were administered to subjects, which vaccines were destroyed at the site, and which vaccines were returned to the Sponsor, as applicable.

- Proper adherence to the local institutional policy with respect to destruction of study vaccines.
- Complete record keeping of study vaccine use, wastage, return or destruction, including documentation of:
 - Copy of the site's procedure for destruction of hazardous material.
 - Number of doses destroyed, date of destruction, destruction code (if available), method of destruction, and name of individual performing destruction.

Vaccines that have been stored differently from the manufacturer's indications **must not** be used unless the Sponsor provides written authorization for use. In the event that the use cannot be authorized, the Sponsor will make every effort to replace the vaccine supply. All vaccines used in conjunction with this protocol must be stored separately from normal hospital/practice stocks to prevent unintentional use of study vaccines outside of the clinical study setting.

Monitoring of vaccine accountability will be performed by the study monitor during site visits and at the completion of the study.

At the conclusion of the study, and as appropriate during the course of the study, the Investigator must ensure that all unused study vaccines, packaging and supplementary labels are destroyed locally (upon approval from Sponsor) or returned to the Sponsor.

7. ASSESSMENTS.

7.1 Safety Assessment

The measures of safety used in this study are routine clinical procedures. They include a close vigilance for, and stringent reporting of, selected local and systemic adverse events routinely monitored in vaccine clinical studies as indicators of reactogenicity.

An adverse event (AE) is defined as any untoward medical occurrence in a subject or clinical investigation subject administered a pharmaceutical product at any dose that does not necessarily have to have a causal relationship with this treatment. Therefore, an AE can be any unfavorable and unintended sign (including an abnormal laboratory finding, for example), symptom, or disease temporally associated with the use of an investigational product, whether or not considered related to the investigational product. This definition includes intercurrent illnesses or injuries and exacerbation of pre-existing conditions.

The period of observation for AEs extends from the time the subject's parent(s)/LAR(s) signs informed consent until he or she completes the specified safety follow-up period Day 181 (for previously vaccinated subjects) or Day 209 (for not previously vaccinated subjects). AEs occurring after the informed consent form is signed but prior to receiving study vaccine/product will be documented as an AE and recorded within source document. However, any AEs occurring prior to receipt of any study vaccine will be analyzed separately from "treatment emergent" AEs (AEs occurring after administration of the first study vaccine).

Adverse events are collected as either solicited or unsolicited adverse events. Solicited events are derived from organized data collection systems, such as the Subject Diary Card(s) or interviews.

7.1.1 Solicited Adverse Events

The term "reactogenicity" refers to solicited signs and symptoms ("solicited adverse events") occurring in the hours and days following a vaccination, to be collected by the subject's parent(s)/LAR(s) for a period of 7 days, using a pre-defined Subject Diary Card.

Each solicited adverse reaction and/or event is to be assessed and entered into the Subject Diary Card (see [Section 3.4.2, Tools used for Data Collection](#) for more details). Each adverse event is to be assessed by the sponsor according a defined severity grading scale (further details are provided in the SAP). The following solicited adverse events are included in the Subject Diary Card.

Solicited local adverse reactions

Injection site:

- Induration (hardness), in mm
- Erythema (redness), in mm
- Ecchymosis (bruising), in mm
- Tenderness, grading:
 - 0=None
 - 1=no interference with daily activity
 - 2=interferes with daily activity
 - 3=prevents daily activity

Solicited systemic adverse events

- Change of eating habits
 - 0=None
 - 1=Eating less than normal for 1 - 2 feeds / meals
 - 2=Missed 1 or 2 feeds / meals
 - 3=Missed more than 2 feeds / meals
- Sleepiness, grading:
 - 0=None
 - 1=shows an increased drowsiness
 - 2=sleeps through feeds / meals
 - 3=sleeps most of the time and it is hard to arouse him/ her
- Vomiting (throwing up)
 - 0=None
 - 1= 1 - 2 times in 24 hours
 - 2= 3 - 5 times in 24 hours
 - 3= 6 or more times in 24 hours or requires intravenous hydration
- Diarrhea (loose stools)
 - 0= Fewer than 2 loose stools in 24 hours
 - 1= 2-3 loose stools in 24 hours
 - 2= 4-5 loose stools in 24 hours
 - 3= 6 or more loose stools in 24 hours or requires intravenous hydration
- Irritability
 - 0=None
 - 1= Requires more cuddling and is less playful than usual
 - 2= More difficult to settle
 - 3= Unable to console

- Shivering
 - 0= None
 - 1= Present but does not interfere with daily activity
 - 2= Interferes with daily activity
 - 3= Prevents daily activity

Other solicited adverse events-related variables

- Fever derived from measured body temperature (defined as $\geq 38.0^{\circ}\text{C}/\geq 100.4^{\circ}\text{F}$). Measurement of temperature with a digital thermometer is preferred. In children younger than 36 months of age, measurement of temperature rectally is preferred. Oral, axillary or tympanic membrane routes may be used in older children.

The study staff must review the data entered into the Subject Diary Card as described in [Section 3.4.2, Tools Used for Data Collection](#) and [Section 5.3.1, Postvaccination Visits](#). All solicited local reactions and solicited systemic adverse events are considered causally related to vaccination.

Note: Any solicited adverse event that meets any of the following criteria must be entered into subjects' source document (see [Section 9.1, Source Documentation](#)) and also as an adverse event on the Adverse Event eCRF:

- Solicited local or systemic adverse event leading to the subject withdrawing from the study or the subject being withdrawn from the study by the Investigator (adverse event leading to withdrawal, see [Section 7.1.3, Evaluation of Adverse Events](#)).
- Solicited local or systemic adverse event that otherwise meets the definition of a serious adverse event (see [Section 7.1.4, Serious Adverse Events](#)).
- If a solicited local reaction or solicited systemic adverse event continues beyond day 7 after vaccination, it will also be recorded as an unsolicited AE on the Adverse Event eCRF.

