Prior to receipt of second study vaccination, subjects must be evaluated to confirm that they are eligible for subsequent vaccination. If subjects meet any of the original exclusion criteria listed above or experienced severe tolerability issues after first study vaccination, they should not receive additional vaccinations. However, these subjects should be encouraged to continue study participation. This review of eligibility should be documented in the source document and the reason for not administering a scheduled study vaccine should be documented in the eCRF.

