7.1.3 Evaluation of Adverse Events

Every effort should be made by the Investigator to evaluate safety information reported by a subject for an underlying diagnosis and to capture this diagnosis as the event in the AE page. In other words, the practice of reporting only symptoms (e.g., "cough" or "ear pain") are better reported according to the underlying cause (e.g., "asthma exacerbation" or "otitis media").

The severity of events reported on the Adverse Events eCRF will be determined by the investigator as:

- Mild: transient with no limitation in normal daily activity.
- Moderate: some limitation in normal daily activity.
- Severe: unable to perform normal daily activity.

The relationship of the study treatment to an AE will be determined by the Investigator based on the following definitions:

1. Not Related

The AE is not related to an investigational vaccine if there is evidence that clearly indicates an alternative explanation. If the subject has not received the vaccine, the timing

of the exposure to the vaccine and the onset of the AE are not reasonably related in time, or other facts, evidence or arguments exist that reasonably suggest an alternative explanation, then the AE is not related.

2. Related

a. Possibly Related

The administration of the investigational vaccine and AE are considered reasonably related in time and the AE could be explained by exposure to the investigational vaccine or by other causes.

b. Probably Related

Exposure to the investigational vaccine and AE are reasonably related in time and no alternative explanation has been identified.

The relationship of the study treatment to an unsolicited AE will be determined by the investigator.

Note: solicited AEs will not be evaluated for relationship to study treatment, as solicited events are by default considered as related to study vaccine in this study. Grading for severity of solicited local and systemic AEs is described in the SAP.

Adverse events will also be evaluated by the investigator for the co-existence of any of the other following conditions:

- “Medically-attended adverse event”: an adverse event requiring hospitalization, or emergency room visit, or visit to/by a health care provider.
- NOCDs: an adverse event that represents a new diagnosis of a chronic medical condition that was not present or suspected in a subject prior to study enrollment.
- AEs leading to withdrawal: adverse events leading to study or vaccine withdrawal.

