6.5.2.3 Analysis of Unsolicited Adverse Events

Definitions

All AEs will be characterized according to the date of occurrence related to the vaccination phase as follows:

- **Non-Treatment Emergent:** start date before the date of injection of study vaccine.
- **Treatment Emergent:** start date on or after the date of injection of study vaccine or, AE increase in severity, including to "serious" AE.

If start date is equal to the first date of injection, then "timing" variable ("Did event start before or after vaccination?") will be used to define whether the AE occur before or after the injection.

If an AE happened on the same day of injection and the time stamp is missing, then the AE is assumed to be treatment emergent.

If an AE start date is missing or unknown, the AE will be considered as emergent.

When start and/or end dates of an AE are only partially known, AEs will be categorized as emergent before, during, or after vaccination phase using the following rules:

- If the partial end date is before (<) the vaccination (i.e., year or year & month is/are before the study vaccination year or year & month) then the AE is not treatment-emergent before vaccination phase.
- If the partial start date is equal or after (≥) the first study vaccination (i.e., year or year & month is/are after or the same as the first study injection year or year & month) then the AE is considered treatment-emergent.

The **maximum event severity** is the greatest severity associated with a PT for a reported AE according to the following order: Mild < Moderate < Severe. Unknown/ Missing severity is considered as severe.

Multiple AEs with the same PT for the same subject are counted only once.

Vaccination-related AEs are those for which the cause has been evaluated by the investigator and recorded as related.

Analysis

This analysis applies to all Treatment-Emergent adverse events occurring during the study, judged either as probably related, possibly related, or not related to vaccination by the investigator, recorded in AE CRF, with a start date on or after the date of first vaccination. AE starting prior to the first vaccination will only be listed.

The original verbatim terms used by investigators to identify AEs in the CRFs will be mapped to preferred terms using the MedDRA dictionary. The AEs will then be

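### The rule that sends solicited reactions to the AE eCRF covers study withdrawal only, while the protocol's own definition of AEs leading to withdrawal also covers vaccine withdrawal, so secondary safety endpoint 3 can be undercounted

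*Protocol*

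**What the plan says.** Section 7.1.1 of the protocol gives three triggers for copying a solicited event to the Adverse Event eCRF. The first is "Solicited local or systemic adverse event leading to the subject withdrawing from the study or the subject being withdrawn from the study by the Investigator"; it cross-refers to Section 7.1.3. The second is "Solicited local or systemic adverse event that otherwise meets the definition of a serious adverse event". The third applies if a reaction "continues beyond day 7 after vaccination, it will also be recorded as an unsolicited AE on the Adverse Event eCRF".

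Section 7.1.3 defines the category as "AEs leading to withdrawal: adverse events leading to study or vaccine withdrawal", without limiting it to unsolicited events.

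Section 4.2 covers eligibility for dose 2. If children have "experienced severe tolerability issues after first study vaccination, they should not receive additional vaccinations". It continues: "However, these subjects should be encouraged to continue study participation". It also asks that "the reason for not administering a scheduled study vaccine should be documented in the eCRF", but does not name the page.

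The only withdrawal flag described for the Adverse Event page is in Section 3.8, and it refers to withdrawal from the study.

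Secondary safety endpoint 3 (protocol 8.1.2.1, SAP 3.2.1) is the percentage of subjects with SAEs, NOCDs or AEs leading to withdrawal over the whole study. SAP 6.5.2.3 builds the withdrawal summary from events "recorded in AE CRF, with a start date on or after the date of first vaccination", as does protocol 8.4.3.1.3. SAP 3.2.1 does not say what the withdrawal is from. SAP 6.5.2.3 names the category only as withdrawal or early termination.

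**The concern.** The definition and the capture rule differ by one term. The definition counts an event that ends vaccination even if the child stays in the study; the capture rule asks for an AE record only if the child leaves the study. Section 4.2 describes children who fall between the two, because it stops dose 2 and at the same time encourages them to remain.

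Solicited reactions are treated as vaccine-related by default (Sections 7.1.1 and 7.1.3). A reaction that ended the vaccine course is therefore directly relevant to a count of AE withdrawals. The solicited-AE tables show that the reaction occurred and how severe it was, but not that it cost the child the second dose. The data are intended to support a licence in this age group, so the count should mean the same thing at every site.

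**Working it through.** The plan states no figure for this point, so the check sets the passages side by side.

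1. Who is exposed. Only children scheduled for two doses (not previously vaccinated) can have dose 2 withheld.

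2. Follow a solicited event that stops dose 2 in a child who stays in the study:
- It is an SAE: it reaches the AE eCRF by the second trigger of Section 7.1.1. This includes the vaccine-related SAEs that bar a further dose under Section 3.8.
- It lasts beyond day 7: it reaches the AE eCRF by the third trigger.
- It is first described verbally and is not on the diary: Section 3.4.2 sends it to the AE eCRF as an unsolicited event.
- It was medically attended: Section 3.8 arguably sends it there. The sentence is not limited to unsolicited events, although it sits in the withdrawal section.
- It is non-serious, on the diary, resolved by day 7 and not otherwise reported: no trigger explicitly applies, although the event meets the Section 7.1.3 definition.

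3. Does other text catch the last case?
- The interviews in Sections 5.2.2 and 5.3.1 ask about AEs leading to study or vaccine withdrawal, but under unsolicited events. Section 7.1.2 defines those as events not solicited by the diary card.
- Section 7.1.5 refers back to Section 7.1.1 for what goes on the AE form, so it adds no route.
- Section 5.5.1 applies study-completion procedures, including questions on AEs leading to withdrawal, when a child is withdrawn from treatment. It applies only when possible and does not say that a diary-recorded reaction must then be entered as an AE. It also ends with an eCRF page that closes the child's participation, which does not fit Section 4.2.
- The reason for withholding dose 2 is recorded (Sections 4.2 and 5.2.2), but no SAP derivation uses it.

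4. Size. The documents give neither the share of two-dose children nor the rate of dose-2 withholding for reactogenicity. To show how far any figure depends on assumption, suppose 70% of 2502 children are in the two-dose group and all other AE withdrawals occur in 0.5% of 2502:
- Two-dose children: 2502 × 0.70 = 1751. Other AE withdrawals: 2502 × 0.005 = 12.5.
- No short reaction stops dose 2: 0 missed.
- 0.1% do: 1751 × 0.001 = 1.75 missed; share 1.75 / (1.75 + 12.5) = 12%.
- 1% do: 1751 × 0.01 = 17.5 missed; share 17.5 / (17.5 + 12.5) = 58%.

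All three rates are assumed, and the calculation supposes that every such case escapes every other route. The result runs from nothing to more than half, so the documents support no estimate.

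**The case against.** The strongest reply is that the first Section 7.1.1 bullet cross-refers to Section 7.1.3, where the wider definition stands, so a careful site would apply that definition. This is a fair reading and makes the text ambiguous rather than plainly exclusionary. It does not remove the problem: the bullet and the Section 3.8 flag both name study withdrawal only, and sites can reasonably differ.

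It is also true that safety is descriptive, with no hypothesis or success criterion, and that the diary reaction is tabulated by maximal severity and vaccine group. A more reactogenic vaccine would show there.

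Four stronger readings may tempt a reader, and the documents do not support them:
- That such reactions never reach the AE eCRF, or that the endpoint misses dose-ending reactions as a class. Serious, prolonged and newly reported verbal events do reach it, and medically attended ones arguably do.
- That no AE record would exist. The eCRF is not among the documents reviewed (the SAP cites its version 0.4), so it may hold a vaccine-withdrawal field. One can say only that the text requires no record.
- That unsolicited events stopping dose 2 are fully counted while solicited ones are not. The visits ask about the former, but the only flag described names study withdrawal for both.
- That the between-arm comparison is biased toward no difference by a known amount. If reactogenicity differs by arm the omissions could be unbalanced, but no direction or size follows from the documents.

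**Conclusion.** The inconsistency is in the text. Protocol 7.1.1 and 3.8 are narrower than 7.1.3, and SAP 3.2.1 and 6.5.2.3 do not say which applies. The gap is confined to two-dose children who remain in the study after dose 2 is withheld for a non-serious, diary-recorded reaction that resolved by day 7 and was not otherwise reported. For them, secondary safety endpoint 3 can be undercounted and recording can vary by site. The conclusion assumes that sites follow Section 7.1.1 literally and that the eCRF has no field that closes the gap. The size is unknown. The solicited-AE endpoint and the noninferiority analyses are unaffected. The correction is worth making because it changes what a named endpoint counts, at little cost.

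**What to change.** - Extend the first trigger in protocol 7.1.1 and the flag in 3.8 to study or vaccine withdrawal, to match 7.1.3.
- Define the category in the same terms in SAP 3.2.1 and 6.5.2.3.
- In the SAP derivation, include children whose recorded eCRF reason for not receiving dose 2 is an adverse reaction.
- Report study withdrawal and vaccine withdrawal as separate lines.
- Reconcile Section 4.2 (child encouraged to continue) with Section 5.5.1 (early-termination procedures, and a page closing participation, on withdrawal from treatment).

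The first four items concern data capture and counting only and leave the criteria for withholding a dose unchanged. The cost is one phrase in the protocol or eCRF guidance and one SAP derivation from data the protocol already asks for. The downside is a slightly higher reported AE-withdrawal rate.
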